## 5.4 Subject Enrollment

Subjects will be provided the IRB/EC approved ICFs and will have the opportunity to read, understand, and have their questions answered prior to signing the ICFs. If the subject agrees to participate in the study and signs consent, the ICF process will be completed. The subject must sign and date the ICF prior to collection of study data. The person reviewing the ICF with the subject will also sign and date the ICFs. The subject will be given copies of the signed ICFs to keep.

Upon entering subject enrollment information into Clindex, each subject will be assigned a unique identification (ID) number sequentially in ascending order. All subjects who sign the ICFs will be documented in a Screening and Enrollment Log. For subjects who sign the ICF but are ineligible to participate, minimum baseline characteristics: age, gender, race, screening date and screen failure reason (s) will be captured in Clindex.

A subject is considered enrolled in the clinical investigation from the moment the subject provides written informed consent and has been confirmed to meet all inclusion criteria and none of the exclusion criteria.

### 5.4.1 Historically Under-Represented Demographic Subgroups

AtriCure will take the following steps to ensure adequate representation of women and racial or ethnic minorities in this clinical investigation:

- as appropriate and necessary, AtriCure will train sites on the importance of recruiting and retaining subjects in the clinical investigation
- approach sites without bias or consideration for specific demographic subgroups
- have informed consent materials in alternative languages and will work with sites and IRBs/ECs on recruitment materials.

## 5.5 Subject Withdrawal

Each enrolled subject shall remain in the clinical investigation until completion of the required follow-up period; however, a subject's participation in any clinical investigation is voluntary and the subject has the right to withdraw at any time without penalty or loss of benefit. Conceivable reasons for discontinuation may include, but not be limited to, the following:

- Subject death
- Subject voluntary withdrawal
- Subject lost-to follow-up as described below
- Subject's follow-up is terminated due to site/study termination

The Sponsor must be notified by the site of the reason(s) for subject discontinuation and record a reason for termination in the case report form (CRF). Investigators must also report this to their respective IRB/EC as defined by their institution's procedure(s).

### Investigator Decision

If the subject experiences an adverse event and the Principal Investigator or Medical Advisor believes it is in their best interest to discontinue participation in the study, they will be withdrawn from the study.

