#### **2.2.4 Device Handling**

Subjects enrolled in this study will already have been treated, therefore device accountability is not required.

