#### Other (which may include)

- Protocol deviation, noncompliance, or violation;
- Investigator/Sponsor recommendation;

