#### Follow-up for Early Terminated Subjects

Given the nature of the study procedures, there are situations where subjects may terminate from the study early that are not described above. No additional follow-up will be required or data recorded from subjects once withdrawn from the clinical investigation, except for the status (deceased/alive). The investigator can use existing data and ask for the subject's permission to collect follow-up data about his/her status/condition including information about device clinical performance or safety. If permission is obtained, the relevant data shall be included in the clinical investigation report.

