## **Safety Endpoint**

Minimal to no missing data are expected for the primary safety endpoint. Based on a PG of 15%, and an expected population MAE rate of up to 8.5%, a sample size of 150 subjects will have 80% power using a one-sided Exact test, with at a one-sided  $\alpha = 0.05$  level of significance.

The highest primary safety endpoint that would meet the PG would be 10% (that is, 15 out of 150 subjects experience at least one MAE).

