### **10.8.1 Study Oversight Committee**

The Study Oversight Committee is comprised of the National PI(s) and Sponsor Medical Advisor. The Chairman of the core laboratories and other sponsor personnel may also participate in the Committee meetings if appropriate. Meeting minutes from this committee will be filed with the sponsor.

The Study Oversight Committee is responsible for overseeing the scientific and operational aspects of the clinical investigation.

Specifically, the committee will participate and/or advise on the following:

- Review of the study protocol
- Review of the training material for the sites as applicable
- Study operations and safety
- Discussion of study related issues with the sites, as needed

- Regulatory communication, as needed

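### Withdrawal after an adverse event by default ends data recording, even when the subject has not withdrawn consent and no study treatment remains to stop

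*Combined protocol and SAP*

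**What the plan says.** Section 5.5, Investigator Decision, names the trigger and who decides: "If the subject experiences an adverse event and the Principal Investigator or Medical Advisor". When either of these two "believes it is in their best interest to discontinue participation in the study, they will be withdrawn from the study", the rule takes effect. It gives no threshold for severity, relatedness or burden. Section 10.8.1 shows whose advisor this is: "The Study Oversight Committee is comprised of the National PI(s) and Sponsor Medical Advisor".

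Section 5.5, under the Other heading, adds protocol deviation, noncompliance or violation as reasons for withdrawal, together with "Investigator/Sponsor recommendation".

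Section 5.5, Follow-up for Early Terminated Subjects, gives the default afterwards: "No additional follow-up will be required or data recorded from subjects once withdrawn from the clinical investigation, except for the status (deceased/alive"). It then softens this: "The investigator can use existing data and ask for the subject's permission to collect follow-up data about his/her status/condition", including device performance and safety, and data obtained that way go into the report. Section 7.5.1 ends safety surveillance when a subject withdraws or concludes participation.

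On treatment, section 2.2.4 states: "Subjects enrolled in this study will already have been treated". Under section 6.2.1, consent is taken 12 to 24 months after the procedure and the monitor is provided then. Baseline, procedure, discharge and 30-day data come from medical records whatever the consent date.

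**The concern.** A rule of this kind suits a trial with ongoing treatment, where leaving the study can spare the subject further exposure. Here, participation after enrollment consists of chart abstraction, one visit (which may be remote) and a 24-hour recording. Withdrawal can relieve the subject of the visit and the recording. It does not require the site to stop reading a chart it already holds, yet the default in section 5.5 is that it does stop.

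The subject in question has not withdrawn consent, but further information depends on the investigator choosing to ask and the subject agreeing again. Missing data can therefore depend on having had an adverse event, and the decision lies partly with the sponsor's advisor in an unblinded single-arm study. The bias measures in section 3.2 (source monitoring, independent adjudication, core lab, random order of invitation) do not cover discretionary withdrawal after enrollment.

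Three kinds of data are exposed:
- the core-lab rhythm result that decides the primary performance endpoint (section 4.2);
- pacemaker implantation and related SAEs through last follow-up (section 4.3);
- attribution of deaths after day 30 (section 4.1). Vital status is kept, but cause and relatedness need records.

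**Working it through.** **The plan's own figures (section 8.3), exact binomial**
- Performance: goal 55%, expected 68%, n = 140, one-sided alpha 0.025. The smallest passing count is 89, since P(X ≥ 89 | 140, 0.55) = 0.0247 and P(X ≥ 88) = 0.0365. Power at 68% is 0.887. Both the stated 89/140 and the stated power above 88% reproduce.
- Attrition 6.5%: 140 / (1 − 0.065) = 149.7, rounded up to 150. Planned loss is 10 of 150.
- Safety: goal 15%, expected 8.5%, n = 150, one-sided alpha 0.05. The largest passing count is 15, since P(X ≤ 15 | 150, 0.15) = 0.0493 and P(X ≤ 16) = 0.081. Power at 8.5% is 0.794, against the stated 80%.

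**What the plan does with a missing rhythm result**

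Section 8.1 defines the ITT population by use of the device, so a withdrawn subject stays in it but has no outcome. Section 8.8 names multiple imputation, LOCF and a tipping-point analysis, all as sensitivity analyses. No rule is given for the primary analysis. The sizing on 140 of 150 is compatible with dropping subjects who have no result, but does not say so.

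**Illustration for performance**

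Assumed, because the documents do not give them: the number lost, k, and the success rate the lost subjects would have had, s. Also assumed: the true rate among all 150 is 55% (the null, 82.5 expected successes), and lost subjects are dropped. The rate among those analysed is then

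p = (82.5 − k·s) / (150 − k),

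and the false-pass rate is P(X ≥ r | 150 − k, p), where r is the exact pass mark for that n.

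| k lost | n | r | s | p | False-pass rate |
|---|---|---|---|---|---|
| 5 | 145 | 92 | 55% | 0.550 | 2.4% |
| 5 | 145 | 92 | 25% | 0.560 | 4.2% |
| 5 | 145 | 92 | 0% | 0.569 | 6.5% |
| 10 | 140 | 89 | 55% | 0.550 | 2.5% |
| 10 | 140 | 89 | 25% | 0.571 | 7.3% |
| 10 | 140 | 89 | 0% | 0.589 | 15.1% |

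The k = 10 rows use up all planned attrition, so within that plan they are an upper bound for loss triggered by adverse events.

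The unstated rule for missing results matters as well. With 89 responders and 10 lost, 89/140 passes. If the 10 count as failures, 89/150 = 59.3% has p = 0.162 and fails, because 95/150 is needed.

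**How long a subject is exposed to the rule**

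If the monitor is issued at consent (section 6.2.1) and the subject exits once the recording is obtained (section 6.2.6), the interval is short. Earlier consent is not clearly excluded: section 6.1 screens anyone within 24 months of the procedure, and section 6.2.7 tells subjects with symptoms before their last visit to contact the site.

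**The case against.** The strongest reply is that the rule is narrower than it looks. Withdrawal needs a best-interest judgement as well as an adverse event. Section 5.5 opens by expecting each subject to stay until follow-up is complete. Existing data remain usable and more can be gathered with permission. The ITT definition does not remove a withdrawn subject, and section 8.8 commits to sensitivity analyses for both primary endpoints. If consent and monitoring coincide, there is little time for the rule to act. Nothing in the documents shows that subjects with adverse events are likelier rhythm failures.

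Most of this stands, and it limits the point to loss that the text permits, not loss that it makes happen. It does not remove the point. Collection after withdrawal is left to the investigator's choice and to a second permission from someone who never withdrew the first. The ITT definition supplies no outcome, and sensitivity analyses do not recover data that could have been abstracted.

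A reader might go further and infer that the rule threatens the 30-day primary safety endpoint, and that it contradicts section 8.3, where "Minimal to no missing data are expected for the primary safety endpoint". The documents do not support that. Under section 6.2.1, days 0 to 30 normally lie well before consent and come from charts, which are naturally existing data. The expectation in section 8.3 fits that source.

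**Conclusion.** The point holds as a modest one that should be corrected. Sections 5.5 and 7.5.1 permit avoidable, adverse-event-linked loss of the rhythm result and of SAE, pacemaker and late-death attribution data through last follow-up, although treatment is complete and consent may still be in force.

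The size is not known. On the assumed scenarios, the nominal 2.5% false-pass rate for performance stays near 2.5% if the lost subjects resemble the rest. If they do worse, it rises to 4.2% or 6.5% with 5 lost, and to 7.3% or 15.1% with 10 lost. These figures rest on dropping the lost subjects and on the assumed success rates. Exposure is small if the monitor is issued at consent and larger if subjects are consented earlier.

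It would be wrong to conclude that the rule could turn a failed safety result into a pass by applying the 6.5% attrition to major adverse events. That attrition is stated for the last follow-up visit and is used to size performance, while the safety calculation uses all 150. Removing subjects from the denominator does not rescue a borderline count either: 15/150 passes (p = 0.049), but 15/147 fails (p = 0.060).

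**What to change.** Keep the investigator's discretion to relieve a subject of the visit or the recording, and change what follows for the data:
- In section 5.5, Follow-up for Early Terminated Subjects, limit the data stop to withdrawal of consent, and align the end of surveillance in section 7.5.1 with it.
- For every other discontinued subject, make chart abstraction through last follow-up the default: SAEs, pacemaker, repeat ablation, any available rhythm data and cause of death. Continue adjudication over the same period.
- Remove protocol deviation and sponsor recommendation as reasons that end data collection.

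As a companion change, the SAP should state how a missing rhythm result counts in the primary performance analysis.

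The cost is protocol and consent wording, plus slightly more data entry from charts the sites already hold.

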### Lost to follow-up

If the subject misses their scheduled follow-up and the attempts at contacting the subject detailed below are unsuccessful, then the subject is considered lost-to-follow-up. Site personnel shall

make all reasonable efforts to locate and communicate with the subject (and document these efforts in the source documents), including the following, at each contact time point:

- A minimum of two telephone calls on different days over the specified follow-up windows to contact the subject should be recorded in the source documentation, including date, time and initials of site personnel trying to make contact.
- If these attempts are unsuccessful, a letter (certified if applicable) should be sent to the subject.

#### Withdrawal of consent

The subject withdraws consent for participation in the study. Any method of contact with the subject in which they state they no longer want to participate in the study specific activities constitutes withdrawal of consent. When possible, the reason for withdrawal will be documented.

Death: Subject expires after enrollment into the study.

#### Site Termination or Study Termination

A site or the study may be terminated. When this occurs all subjects at the site will be withdrawn and documented as early termination. Reasons for site or study termination may include, but are not limited to the following:

- Administrative concerns (e.g., inadequate subject enrollment, Investigator/institution non-compliance, change of business strategy, etc.);
- Safety issues, including those due to non-compliance, which substantially affect the risk to benefit ratio of the study subjects at a site or for the study as a whole;
- Regulatory body mandate(s).

#### Other (which may include)

- Protocol deviation, noncompliance, or violation;
- Investigator/Sponsor recommendation;

#### Follow-up for Early Terminated Subjects

Given the nature of the study procedures, there are situations where subjects may terminate from the study early that are not described above. No additional follow-up will be required or data recorded from subjects once withdrawn from the clinical investigation, except for the status (deceased/alive). The investigator can use existing data and ask for the subject's permission to collect follow-up data about his/her status/condition including information about device clinical performance or safety. If permission is obtained, the relevant data shall be included in the clinical investigation report.

### **5.6 Number of Subjects**

Up to 150 subjects will be enrolled at up to 20 sites in the US, UK and/or EU.

### **5.7 Total Expected Duration of the Clinical Investigation**

The expected duration of the study is approximately 21 months. Enrollment will be closely monitored and AtriCure will work directly with the sites to clearly understand the enrollment challenges they might be facing, retrain as needed and pursue other strategies to redress any enrollment lapse. Subjects will be exited from the trial at the conclusion of their primary performance follow-up visit occurring at least 12-months post-procedure.

## **6 TREATMENT AND EVALUATION OF ENDPOINTS**

### **6.1 Study Eligibility**

All subjects recruited for study enrollment must meet all study enrollment criteria prior to being enrolled in the study. The clinical investigation site will review all subjects treated with the CRYOF surgical ablation system, and who are within 24-months post-procedure for study eligibility. Once the initial chart review indicates that the subject meets the study inclusion / exclusion criteria, the subject will be approached for their interest in the study, including willingness to return for their follow-up visit.

### **6.2 Follow-up Assessments**

#### **6.2.1 12-Month Visit ( $\geq$ 12-months but $\leq$ 24-months post index ablation procedure)**

Subjects will be consented 12 to 24 months post procedure and will be provided with a 24-Hour rhythm monitoring device at that time. The post procedure follow-up assessment will include:

- NYHA Classification
- 24-Hr Rhythm Assessment
- Evaluation of AEs/SAEs
- Medications – class I and III AAD's and anticoagulants, including any adjustments
- Review cardioversion since last visit

Note: If a clinical site is capable of remote subject visits, a modified visit assessment may be conducted. Remote subject visits should include Telemedicine appointments with the Investigator, where feasible, to allow direct engagement with the study subject and to ensure complete data collection. Rhythm monitoring devices may be provided to the subject either during an in-clinic follow-up visit, or shipped to the subject for a remote follow-up visit as applicable.

If clinical site is NOT able to perform remote subject visits, an attempt will be made to schedule the study subject visit as close to the visit window as is possible.

Regardless of when the subject is consented, the following data will be collected by reviewing the subjects' medical records retrospectively. For retrospective visits that fall outside of the required windows, please refer to sections 6.2.9 (Unscheduled Visit) and 10.6 (Protocol Deviations).

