#### Coronary Sinus lesion

Lesion	Endo/Epi	Device(s)	Minimum Duration
Epicardial lesion down to the level of mitral valve annulus with the inclusion of coronary sinus. **Ensure removal of retrograde cannula prior to lesion	Epi	CRYOF	2 min

If, for whatever reason, not all above mentioned lesions were performed, data will be collected on the actual lesions performed in order to allow subgroup analysis of patients that received the optimum lesion set, against patient that received a sub-optimum lesion set.

The LAA, however, should have been managed/excluded in all subjects ideally using the AtriCure AtriClip ACH1, ACH2, or FLEX V devices. Suture techniques are allowed as well.

The follow-up assessment data will be entered into the EDC developed for the study.

Documentation and reason for screen failure (i.e., inability to consent, refused consent, did not meet inclusion exclusion criteria, death or major morbidity (such as stroke) etc.) will be secured on a screening log within the EDC.

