### **5 SUBJECT SELECTION AND WITHDRAWAL**

#### **5.1 Subject Population**

This clinical investigation will enroll patients who have undergone concomitant surgical AF ablation using the CRYOF device. Subjects must meet all eligibility criteria and provide written informed consent prior to collection of study data.

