### **5.3.2 Inclusion Criteria**

#### **5.3.2.1 General Inclusion Criteria**

All subjects recruited for study participation must meet all of the following inclusion criteria to be enrolled in the study:

1. Subject is greater than or equal to 18 years of age.
2. Subject has documented history of atrial fibrillation.
3. Subjects who received surgical ablation for their atrial fibrillation using CRYOF and on whom at least the following lesions were performed: left and right pulmonary vein isolation, roof and floor lines, mitral annulus line, a connecting lesion from left atrial appendage to left pulmonary vein, coronary sinus lesion, and LAA exclusion, with a lesion duration of at least 2 minutes.
4. Stable subject that underwent non-emergent cardiac surgical procedure(s) on cardiopulmonary bypass including open-heart surgery for one or more of the

following: mitral valve repair or replacement, aortic valve repair or replacement, tricuspid valve repair or replacement, and coronary artery bypass procedures, or atrial septal defect (ASD) repair.

5. Left Ventricular Ejection Fraction  $\geq 30\%$  (determined by echocardiography or cardiac catheterization performed within 90 days of enrollment as documented in subject medical history).
6. Subject is willing and able to provide written informed consent.
7. Subject is willing and able to return for scheduled follow-up visits.

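### Consent 12 to 24 months after surgery makes 30-day deaths unobservable in the co-primary safety endpoint, and no visible analysis or scope statement deals with this

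*Combined protocol and SAP*

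**What the plan says.** - **Timing of consent.** Section 6.2.1: "Subjects will be consented 12 to 24 months post procedure and will be provided with a 24-Hour rhythm monitoring device at that time".
- **Treatment comes first.** Section 2.2.4: "Subjects enrolled in this study will already have been treated, therefore device accountability is not required".
- **Consent defines enrolment and precedes data.** Section 5.4: "A subject is considered enrolled in the clinical investigation from the moment the subject provides written informed consent". Section 5.1: "Subjects must meet all eligibility criteria and provide written informed consent prior to collection of study data".
- **The patient must be able to take part.** Inclusion 6: "Subject is willing and able to provide written informed consent". Inclusion 7: "Subject is willing and able to return for scheduled follow-up visits". Section 5.2.2.1 excludes incapacitated people; it provides for a representative to sign the consent form in the case of people who cannot read or write.
- **The endpoint.** Section 4.1 is a 30-day composite of death, stroke, myocardial infarction and major bleeding. I read its opening words as restricting it to events related to the ablation procedure. Section 8.2.2 tests the event rate against 15%, and section 8.10 makes that test necessary for trial success.
- **Deaths before enrolment.** Section 3.1 lists among the screen-failure reasons "did not meet inclusion exclusion criteria, death or major morbidity (such as stroke) etc", and section 5.2.1 does the same. In section 5.5, death as a reason for leaving the study is "Subject expires after enrollment into the study".
- **Analysis population.** Section 8.1 defines ITT by use of the device and makes it primary for safety. Section 8.3 expects almost no missing safety data. Section 8.8 plans sensitivity analyses for missing data, with details left to a SAP.

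**The concern.** The safety endpoint names death, but the enrolment rules admit only people alive and able to consent at least a year after the 30-day window opened. A passing result would be read as evidence on a composite that includes death, when no death in the window could have been recorded. Section 1.1.5 says the data are meant for regulatory submissions, so this reading matters.

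Section 8.1 adds to the problem by describing the population as everyone on whom the device was used. Only consenting survivors can be in it. Patients who were never enrolled are not missing data in the sense of section 8.8, so the analyses planned there would not bring them back. The bias measure in section 3.2, random order of invitation, is aimed at temporal bias and does not mention survival.

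**Working it through.** **1. Which components can be observed**

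| Component (4.1) | Can it be counted in an enrolled subject? |
|---|---|
| Death by day 30 | No, if consent comes at 12 to 24 months. If consent came earlier, only deaths after consent could count. |
| Stroke | In part. A survivor able to consent can be counted. Losses arise through the screen-failure route, through incapacity (5.2.2.1), and through exclusion 5 if prior stroke is judged at screening. Placing eligibility at Baseline (6.2.2, 6.2.8) favours judging it before surgery. |
| Major bleeding | Mostly, but exclusion 25 may remove bleeds that led to cardiac re-operation. |
| Myocardial infarction | Yes, in survivors who consent. |

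**2. The plan's own safety figures**

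Inputs from section 8.3: n = 150, goal 15%, expected rate 8.5%, one-sided exact test at 0.05.

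- P(X ≤ 15 | 150, 0.15) = 0.0493 and P(X ≤ 16 | 150, 0.15) = 0.0807, so 15 is the largest passing count, as stated.
- Power = P(X ≤ 15 | 150, 0.085) = 79.4%, against 80% stated.

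The design reproduces. Its 4.9% size refers to the population from which the 150 are drawn.

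**3. What selection could do to the error rate**

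The documents give no rate for these losses, so *d* and *u* below are assumptions. Let the true event rate among all treated patients be 15%. Let *d* be the share of treated patients who had a qualifying event and cannot be enrolled, and *u* the share who were event-free and cannot be enrolled, for example because of a later unrelated death.

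Rate among those who can be enrolled: r = (0.15 − d) / (1 − d − u). Chance of passing: P(X ≤ 15 | 150, r).

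| | d = 0.5 points | d = 1 point | d = 2 points |
|---|---|---|---|
| u = 0 | r = 14.57%, 6.5% | r = 14.14%, 8.6% | r = 13.27%, 14.4% |
| u = 3 points | r = 15.03%, 4.8% | r = 14.58%, 6.5% | r = 13.68%, 11.3% |
| u = 5 points | r = 15.34%, 3.9% | r = 14.89%, 5.3% | r = 13.98%, 9.5% |

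Break-even: r = 0.15 when 0.85d = 0.15u, that is u = 5.67d. The chance of passing exceeds 4.9% only if fewer than 5.67 event-free patients are lost for each event patient lost, which means the event rate among the lost is above 15%.

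**4. Adding unseen patients back to an observed result** (p = P(X ≤ x | n, 0.15))

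| Start | Add | Result |
|---|---|---|
| 15/150, p = 0.049 | 1 event | 16/151, p = 0.076, fails |
| 15/150 | 1 event, 7 event-free | 16/158, p = 0.049, passes |
| 13/150, p = 0.015 | 2 events | 15/152, p = 0.043, passes |
| 13/150 | 3 events | 16/153, p = 0.067, fails |
| 13/150 | 3 events, 5 event-free | 16/158, p = 0.049, passes |

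At the expected 8.5%, about 13 events are anticipated (150 × 0.085 = 12.75). Adding back event patients alone is therefore a worst case; a fair add-back also needs the event-free patients who were lost.

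**The case against.** **Consent timing is not uniform.** Sections 3.1 and 6.1 speak of patients within 24 months of surgery, section 6.2.8 puts consent at Baseline, and section 6.2.1 itself later allows for consent at varying times. Unscheduled visits before the last visit (6.2.7), safety surveillance from enrolment to the 12-month visit (7.5.1), loss to follow-up (5.5) and 6.5% attrition (8.3) also fit poorly with consent only at the final visit. This stands as a reason to reconcile the text, and it limits the absolute claim to section 6.2.1 as written. It does not remove the problem: consent follows treatment on any reading, so deaths before consent are always excluded.

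**A SAP not included here may deal with it.** Sections 4.5, 8 and 8.8 allow for one, so I claim only that nothing visible does. A SAP could not easily repair the matter without outcome data on patients who were not enrolled.

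**Inflation is not demonstrated.** Correct. Two of the nine scenarios fall below 4.9%. The endpoint counts only ablation-related deaths, and section 7.4 separates general surgical events, so *d* is narrower than surgical mortality. For this reason I do not rest the conclusion on those figures.

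**Part of the machinery exists.** Sites review all treated patients (6.1), invitations are randomly ordered (3.2) and deaths are logged (3.1, 5.2.1). This makes the remedy cheaper; it does not replace an analysis or a scope statement.

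**Conclusion.** The concern holds and should be corrected before the safety result is relied on. As section 6.2.1 is written, death within 30 days cannot occur in an enrolled subject, although it is a named component of an endpoint that must succeed. If consent may come earlier, the loss is limited to deaths before consent, but it is still systematic. The safety test is valid at 4.9% for patients who survived and consented, and the plan does not say that its conclusion is limited to them.

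The direction and size of any bias for all treated patients depend on assumed losses: a pass probability of 3.9% to 14.4% over the range examined, against 4.9%. The seriousness lies in the unobservable component and the unstated scope, which follow from the protocol text alone.

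**What to change.** 1. **Reconcile the text.** Give one consent timing across sections 3.1, 6.1, 6.2.1 and 6.2.8. Tie exclusion 5 to the time before the index ablation. As lesser points, state how exclusion 25 treats re-operation for a 30-day bleed, and replace the undefined safety-population label in section 8.2.2, which names ITT in its next sentence.
2. **Capture the unseen patients.** State that the random list in section 3.2 is drawn from all treated patients before vital status is known. For selected, otherwise eligible patients who are not enrolled, record on the screening log: vital status; the date, cause and relatedness of any 30-day death or stroke; and whether records show any other section 4.1 event.
3. **Prespecify a supportive analysis** of 30-day safety over all selected, otherwise eligible patients. Count events adjudicated as related, and put non-enrolled patients whose records show no event in the denominator. Report separately those whose records cannot be reviewed, and do not treat them as event-free. Beside it, give a bound that adds event patients only and counts every death, labelled a worst case because it departs from the relatedness rule in section 4.1.
4. **In any case,** state that the primary safety conclusion applies to patients who survived and consented, and report the logged deaths and strokes next to it.

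**Cost.** Protocol wording, a few log fields and one supportive analysis; the sample size and primary test do not change. Recording details on patients who did not consent conflicts with section 5.1 as written and may need IRB/EC agreement. Adjudication will be limited by the available records, and the event rate may look less favourable. Item 4 costs almost nothing.
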